8.2.5 Clinical Laboratory and Urinalysis

Clinical laboratory assessments include hematology, clinical chemistry, coagulation, lipid panel, thyroid panel, LH, FSH, SHBG, renin, aldosterone, inhibin B for males only, and estradiol, prolactin, and progesterone for females only. eGFR for screening will be calculated from blood creatinine measured as part of screening clinical chemistry.

A complete list of study-required clinical laboratory and urinalysis tests is provided in [Section 13.3](#).

All study-required clinical laboratory tests must be conducted in accordance with the laboratory manual and will be performed by a central laboratory.

The Investigator must review the laboratory report, document the review, and record any clinically significant laboratory findings that occur during the study in the AE section of the eCRF. Laboratory reports must be filed with the source documents. Clinically significant laboratory findings are those that are not associated with the underlying disease, unless judged by the Investigator to be more severe than expected for the subject's condition.

All laboratory tests with values considered clinically significantly during the Treatment Period or within 30 days after the last dose of study drug should be reported as AEs and repeated at least weekly until the values return to normal or baseline or are no longer considered clinically significant by the Investigator or Medical Monitor. If such values do not return to normal/baseline within a period of time judged reasonable by the Investigator, the etiology should be identified, and the Sponsor notified.

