13.2.2 Increased Liver Chemistry Monitoring While Continuing Study Drug

If ALT \geq 3x ULN and $<$ 5x ULN **and** total bilirubin $<$ 2x ULN, **without** symptoms believed to be related to liver injury or hypersensitivity, **and** the subject can be monitored weekly for 4 weeks, perform the following actions:

- Notify the Medical Monitor within **24 hours** of learning of the abnormality to discuss subject safety.
- Subject can continue study drug.

- Collect blood samples weekly for repeat liver chemistry tests (ALT, AST, ALP, GGT, bilirubin, total bile acids, PT/INR, and PTT) until the abnormalities resolve, stabilize, or return to baseline.
- If at any time the subject meets liver chemistry stopping criteria, proceed as described in [Section 7.1.1](#) and [Section 13.2.1](#).
- If, after 4 weeks of monitoring, ALT <3x ULN and total bilirubin <2x ULN, monitor per standard scheduling for remainder of study and follow-up period.

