8.4 Analysis Windows

Clinical visits may occur outside protocol-specified windows. Therefore, instead of relying solely on visit labels in the clinical database, analysis visits and their windows are defined using Enrollment Day or Study Day. For the purposes of data analysis and summary, assessments and/or measurements will be flagged based on the collection date/time that is closest to the protocol-scheduled time point (or Target Study Day). Analysis visit windows are presented in by type of assessments and/or measurements.

Table 12 Visit Analysis Windows (Clinic visits only)

Protocol Specified Visit Number	Analysis Visit	Reference Study Day	Target Study Day	Start (days)	Stop (days)
Visit 1 (Screening)	Screening	Enrollment Day	-114	low	-7
Visit 2	Week -12	Enrollment Day	-84	-6	15
Visit 3	Week -8	Enrollment Day	-56	16	50
Visit 4	Week -2	Enrollment Day	-14	51	high
Visit 5	Day 1	Study Day	1	-6	7
Visit 6	Week 3	Study Day	22	8	32
Visit 7	Week 6	Study Day	43	33	64
Visit 8	Week 12	Study Day	85	65	106
Visit 9	Week 18	Study Day	127	107	148
Visit 10	Week 24	Study Day	169	149	197
Visit 11	Week 32	Study Day	225	198	253
Visit 12	Week 40	Study Day	281	254	323
Visit 13	Week 52	Study Day	366	324	408
Visit 14	Week 64	Study Day	450	409	492
Visit 15 or Extension Visit 1	Week 76	Study Day	534	493	high or 575
Extension Visit 2	Week 88	Study Day	617	576	659
Extension Visit 3	Week 100	Study Day	701	660	785
Extension Visit 4	Week 124	Study Day	869	786	953
Extension Visit 5	Week 148	Study Day	1037	954	1121
Extension Visit 6	Week 172	Study Day	1205	1122	1289
Extension Visit 7	Week 196	Study Day	1373	1290	1457
Extension Visit 8	Week 220	Study Day	1541	1458	1625
Extension Visit 9	Week 244	Study Day	1709	1626	1793
Extension Visit 10	Week 268	Study Day	1877	1794	1961
Extension Visit 11	Week 292	Study Day	2046	1962	2129
Extension Visit 12	Week 316	Study Day	2213	2130	2228
Visit 16 or Extension Visit 13 (follow up)	Follow-up	Study Day		Last dose +1	Last dose +30

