9.3.2 Handling of Laboratory Data

For laboratory data, a missing baseline value will be replaced with the last available assessment, generally the screening assessment. A retest value will be used if the first test is invalidated, e.g., specimen hemolyzed. For non-PK laboratory values that are continuous in nature but are presented as either above or below the respective quantitation limits, the following imputations will be made for the purposes of summarization:

- If value is listed as $< X$, then the imputed value will be $X/2$
- If a value is listed as $\leq X$, then the imputed value will be X
- If value is listed as $> X$, then the imputed value will be $X+1$
- If a value is listed as $\geq X$, then the imputed value will be X

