13.2 Clinical Laboratory Evaluation

[Table 17](#) shows clinical laboratory assessments (hematology, chemistry, lipid panel, thyroid panel, urinalysis, and other tests) will be performed. Laboratory parameters will be summarized

by treatment and post-baseline scheduled time point, based on actual treatment received at each scheduled time point.

Table 17 Clinical Laboratory Parameters

Chemistry	Hematology	Urinalysis	Thyroid
Glucose, fasting	Platelet count	Specific gravity	T3
Potassium	RBC count	pH	T4
Calcium	MCV	Glucose	TSH
Sodium	MCH	Protein	
BUN	% reticulocytes	Blood	
Creatinine	Hemoglobin	Ketones	Other
Total protein	Hematocrit	Bilirubin	LH
ALP	WBC count	Urobilinogen	FSH
ALT/SGPT	Neutrophils	Nitrite	SHBG
AST/SGOT	Lymphocytes	Microscopic examination	Renin
GGT	Monocytes		Aldosterone
Total bilirubin	Eosinophils		Male: Inhibin B
Direct bilirubin	Basophils	Lipid	Female: Estradiol
Total bile acids		Total cholesterol	Female: Prolactin
PT/INR		LDL	Female: Progesterone
PTT		HDL	Hy's Law
		Triglycerides	

Numeric results will be summarized using (8-point) descriptive statistics at baseline and at each scheduled post-baseline time point, unless otherwise specified. Changes from baseline at randomization will also be summarized by scheduled time point.

In addition, the number and percentage of subjects with potentially clinically significant abnormalities (PCSA, see [Table 18](#)) in selected chemistry and hematology parameters (i.e., above the specified upper limit or below the specified limit) will be summarized by scheduled time point.

The number and percentage of subjects who meet criteria for potential drug-induced liver injury as defined by Hy's law will also be summarized.

Table 18 Potentially Clinically Significant Abnormalities by Laboratory Parameter

Parameter	PCSA Low	PCSA High
Chemistry		
ALT		>3 x ULN
AST		>3 x ULN
ALP		>1.5 x ULN
Total Bilirubin		>1.5 x ULN
Total bile acids		> 10 $\mu\text{mol}/\text{L}$
Creatinine		> 1.8 mg/dL or > 0.4 mg/dL increase from baseline ($> 159.16 \mu\text{mol}/\text{L}$ or $> 35.37 \mu\text{mol}/\text{L}$ increase from baseline)
Sodium	< 130 mEq/L ($< 130 \text{ mmol}/\text{L}$)	>150 mEq/L ($> 150 \text{ mmol}/\text{L}$)
Glucose	< 3 mmol/L ($< 54 \text{ mg}/\text{dL}$)	
Potassium	< 3 mEq/L ($< 3 \text{ mmol}/\text{L}$)	$\geq 5.5 \text{ mEq}/\text{L}$ ($> 5.5 \text{ mmol}/\text{L}$)
Calcium		>11.4 mg/dL ($> 2.84 \text{ mmol}/\text{L}$)

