BUN		> 30 mg/dL and > 10 mg/dL increase from baseline ($> 10.71 \text{ mmol}/\text{L}$ and $> 3.57 \text{ mmol}/\text{L}$)
INR		>1.5 x ULN
Total Bile Acids		>5 x ULN or >3 x ULN if ALT is >3 x ULN
FSH		>15 IU/L if baseline was <5 IU/L
Hematology		
Hemoglobin		$\leq 10 \text{ g}/\text{dL}$ and >2 g/dL reduction from baseline ($\leq 100 \text{ g}/\text{L}$ and $> 20 \text{ g}/\text{L}$)
Leukocytes		<500/ μL ($< 0.5 \times 10^9/\text{L}$)
Neutrophils		<1800/ μL and >500/ μL reduction from baseline
Platelets		<50,000/ μL ($< 50 \times 10^9/\text{L}$)

All laboratory results will be listed with reference ranges and range indicator (Low, High, or Clinically Significantly Abnormal). In addition, laboratory results that meet or exceed the pre-specified PCSA levels (Table 19) will be flagged.

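### The laboratory and ECG threshold tables count subjects visit by visit and give no per-arm total of subjects ever abnormal

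*SAP*

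**What the plan says.** **Threshold counts.** SAP 13.2 gives the number and percentage of subjects with Table 18 abnormalities (ALT, AST, ALP, bilirubin, bile acids, INR and others), values "above the specified upper limit or below the specified limit) will be summarized by scheduled time point". SAP 13.4 does the same for the Table 20 ECG levels. The matching sentence for vital signs in SAP 13.3 carries no visit restriction.

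**Which record is used.** Under SAP 8.4, "assessments and/or measurements will be flagged based on the collection date/time that is closest to the protocol-scheduled time point". SAP 9.3.2 adds only that "A retest value will be used if the first test is invalidated"; it has no worst-value rule.

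**Where off-schedule values come from.** Protocol 13.2.2, for ALT from 3x to below 5x ULN with study drug continuing, says "Collect blood samples weekly for repeat liver chemistry tests". Protocol 8.2.5 has clinically significant results "repeated at least weekly until the values return to normal" or baseline, or until no longer clinically significant.

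**Other outputs.** SAP 13.2 continues: "The number and percentage of subjects who meet criteria for potential drug-induced liver injury as defined by Hy's law will also be summarized". It also says "All laboratory results will be listed with reference ranges and range indicator", with flags for values beyond the pre-specified limits. SAP 13.1.2 plans a table of liver AESIs alongside the general adverse-event tables by treatment group.

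**What the protocol asked for.** Protocol 9.4.7.4 leaves the summary of subjects meeting laboratory thresholds to the SAP, and foresees p-values for differences in the proportions meeting them.

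**The concern.** Transient liver-test elevation is the clinical risk that the protocol singles out. Protocol 2.2.5 reports two Phase 2 subjects with it, at doses above the one used here, and the benefit-risk argument in Protocol 2.3.3 relies on monitoring for it. The natural safety question is how many subjects in each arm ever crossed a given limit. A table split by visit does not answer it. Elevations in different subjects at different visits sit in different rows, and rows cannot be added without knowing which subjects recur. Selecting the record nearest the target day can also leave out values from the extra draws made because something looked abnormal. A modest imbalance between arms could then be hard to see in the tables meant to show it.

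**Working it through.** The plan states no figure to reproduce here. The check applies the SAP 8.4 rule to the schedule and then compares the two ways of counting.

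**1. Windows (SAP Table 12), double-blind period.** Length = stop − start + 1.

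| Visit | Target day | Window | Length (days) |
|---|---|---|---|
| Week 3 | 22 | 8–32 | 25 |
| Week 6 | 43 | 33–64 | 32 |
| Week 12 | 85 | 65–106 | 42 |
| Week 18 | 127 | 107–148 | 42 |
| Week 24 | 169 | 149–197 | 49 |

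One record is used from each window.

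**2. Do weekly repeats reach the table?** Assume that each scheduled sample is drawn on its target day and followed by four weekly repeats.

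- After Day 22: 29, 36, 43, 50. Day 43 is the scheduled Week 6 day; the others are 7 days from target.
- After Day 43: 50, 57, 64, 71. The first three are 7, 14 and 21 days from the Week 6 target; Day 71 is 14 days from the Week 12 target.
- After Day 85: 92, 99, 106, 113. Same distances, with Day 113 falling in the Week 18 window.
- After Day 127: 134, 141, 148, 155. Same distances, with Day 155 falling in the Week 24 window.
- After Day 169: 176, 183, 190, 197. These are 7, 14, 21 and 28 days from target.

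The scheduled sample is always at distance 0, so none of the extra repeats is selected. This depends on the on-target assumption. If the Week 6 sample were drawn six days late, on Day 49, a Day 43 repeat would be the record used.

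**3. By visit against by subject.** Take 45 per arm (the planned size, SAP 6) and the five post-baseline double-blind visits. Suppose five tildacerfont subjects each have one elevation, at different visits, and placebo has none.

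- By visit: 1/45 = 2.2% in each of five rows, against 0/45; Fisher two-sided p = 1.0.
- By subject: 5/45 = 11.1% against 0/45; Fisher two-sided p = 2 × (45·44·43·42·41)/(90·89·88·87·86) = 2 × 0.0278 = 0.056.

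The same five rows of 1/45 would also arise if one subject were elevated at all five visits, when the per-subject figure is 1/45. The by-visit table cannot tell these cases apart.

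**4. Range under assumed rates.** With per-visit probability p, independent across five visits, the proportion ever abnormal is 1 − (1 − p)^5:

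| p per visit | Ever abnormal |
|---|---|
| 1% | 4.9% |
| 2% | 9.6% |
| 3% | 14.1% |
| 5% | 22.6% |

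Correlated elevations within a subject would narrow the gap.

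**5. Do the other outputs fill it?**

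- The Hy's law count is per subject with no visit restriction, but it needs a combination of abnormalities. An isolated ALT rise does not qualify, and the SAP does not say which records feed the count.
- The liver AESI table counts subjects by arm. Protocol 8.3.8 says only that the listed events may be AESIs, and SAP 8.3.22 limits AESIs to events not meeting SAE criteria. It is not a fixed-threshold count.
- Adverse-event tables include a laboratory value when it is judged clinically significant (Protocol 8.2.5).
- Listings show every value but give no proportion by arm. The flag sentence cites Table 19, which holds the vital-sign limits; the laboratory limits are in Table 18.

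**The case against.** Much of the case on the other side stands. The gravest combined liver signal has its own per-subject count. Liver AESIs and adverse events are tabulated by arm, whether or not the sample was scheduled, and events meeting stopping criteria are entered as AESIs under Protocol 13.2.1.1. The weekly repeats in Protocol 13.2.2 start from an ALT already at or above 3x ULN. If a scheduled sample showed that, the subject is normally already counted, and Table 18 has no higher ALT tier for a later peak to reach. Double-blind laboratory visits are 3 to 6 weeks apart; the longer gaps fall in the open-label period, where there is no concurrent placebo arm. Protocol 2.3.1 reports no liver-test abnormalities in CAH subjects at 200 mg QD or less over 2 weeks. A DSMB that includes a hepatologist sees unblinded safety data. QTcF above 500 msec or a rise above 60 msec gets a separate listing. SAP 8 places presentation conventions in mock shells that are not available here and might contain the missing row.

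A reader might infer that unscheduled liver peaks vanish from all by-arm reporting, or that any event seen only at an unscheduled draw counts as zero. The documents do not support either. The AESI and adverse-event tables can carry such events, and SAP 8.4 assigns windows by study day, so an unscheduled draw is used when it is closest to target, for example when the scheduled draw is missed.

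None of this supplies a count by arm of subjects who ever crossed a Table 18 or Table 20 limit.

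**Conclusion.** The point holds for the threshold tables in SAP 13.2 and 13.4, not for liver safety reporting as a whole. As written, those tables give no per-arm total of subjects ever abnormal. They can miss abnormalities first seen off schedule, and bilirubin, INR or bile-acid abnormalities that appear only on repeat. The by-subject total is lost even if no unscheduled sample is ever taken.

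The size is unknown. The contrast of 2.2% per row with 11.1% per subject is a constructed case at the far end, with five different subjects at five different visits. The p-value of 0.056 belongs to that construction and is not evidence of an imbalance. The finding that no extra repeat is selected assumes on-target scheduled draws. This is a cheap improvement to safety reporting; it does not touch the efficacy conclusions.

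**What to change.** In SAP 13.2 and 13.4, for each Table 18 and Table 20 threshold, add the number and percentage of subjects whose worst post-baseline value meets it. Present this by treatment and study period, and use scheduled, unscheduled and early-termination results. Keep the by-visit tables as supportive. State that the Hy's law count uses the same set of records. Correct the listing-flag reference in SAP 13.2 from Table 19 to Table 18.

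The cost is a few lines of SAP text and one extra table from data already collected. No visit, sample or clinical rule changes.

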13.5 Physical Examination

Abnormal clinically significant findings from physical examinations are reported as AEs.

13.6 Psychiatric Evaluations

13.6.1 The Hospital Anxiety and Depression Scale

The HADS is a self-assessment questionnaire for detecting states of anxiety and depression in subjects in clinical trials. The total score of HADS, change from baseline in total score will be summarized by time point, treatment group, and study period.

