5.1.2 Exclusion Criteria

A subject will not be eligible for this study if he/she meets any of the following criteria:

1. Has a known or suspected diagnosis of any other known form of classic CAH (not due to 21-hydroxylase deficiency)
2. Has a history that includes bilateral adrenalectomy or hypopituitarism
3. Has a history of allergy or hypersensitivity to tildacerfont, any of its excipients, or any other CRF₁ receptor antagonist
4. Shows clinical signs or symptoms of adrenal insufficiency
5. Has had a clinically significant unstable medical condition, medically significant illness, or chronic disease occurring within 30 days of screening, including but not limited to:
 - a. An ongoing malignancy or <3 years of remission history from any malignancy, other than successfully treated localized skin cancer
 - b. eGFR of <45 mL/min/1.73 m²
 - c. Current or history of liver disease (with the exception of Gilbert's syndrome)
 - d. History of alcohol or substance abuse within the last year, or any significant history of alcohol or substance abuse that would likely prevent the subject from reliably participating in the study, based on the opinion of the Investigator
 - e. Active hepatitis B, hepatitis C, or HIV at screening
 - f. Subjects who plan to undergo bariatric surgery during the study are excluded
 - g. Any other condition that would impact subject safety or confound interpretation of study results
6. Psychiatric conditions, including but not limited to bipolar disorder, schizophrenia, or schizoaffective disorders that are not effectively controlled on medication and may have an adverse impact on study compliance. Symptoms including hallucinations, delusions, and psychosis are exclusionary. Additionally:

- a. Increased risk of suicide based on the Investigator's judgment or the results of the C-SSRS conducted at screening and baseline (eg, C-SSRS Type 3, 4, or 5 ideation within the past 6 months or any suicidal behavior within the past 12 months)
- b. HADS score >12 for either depression or anxiety at screening or baseline
7. Has clinically significant abnormal ECG or clinical laboratory results. Abnormal results that must be reviewed and discussed with the Medical Monitor to determine eligibility for this study include but are not limited to:
 - a. Any clinically meaningful abnormal ECG results, including QTcF >450 ms for male participants or >470 ms for female participants
 - b. ALT >2x ULN
 - c. Total bilirubin >1.5x ULN

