7.1.4 Depression or Anxiety Stopping Criteria

Individuals who score >12 on either the depression or anxiety subscale of the HADS (see [Section 8.2.6.2](#)) at screening or baseline are not eligible for this study. Any subject who develops severe depression or anxiety (Common Terminology Criteria for Adverse Events [CTCAE] Grade 3 or higher), as assessed by the Investigator, will require study drug discontinuation and appropriate follow-up. This will be considered an AESI if it is not an SAE (eg, requiring hospitalization) (see [Section 8.3.8](#)).

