8.2.6 Psychiatric Evaluations

8.2.6.1 *Columbia–Suicide Severity Rating Scale*

The C-SSRS will be used during the study to monitor suicidal ideation and behavior. The C-SSRS is a Food and Drug Administration (FDA)–endorsed questionnaire administered by trained study personnel to screen for suicidality in trials of CNS-active compounds. The Baseline/Screening Version of the C-SSRS, which assesses both lifetime history and history from the last 12 months, will be used at screening to determine subject eligibility. The Since Last Visit Version of the C-SSRS will be used at all subsequent visits specified.

Refer to [Section 7.1.3](#) for suicidality individual treatment-stopping criteria.

8.2.6.2 *Hospital Anxiety and Depression Scale*

Subject anxiety and depression will be monitored during the study using the HADS, assessed at baseline and Weeks 12, 24, 52, and 76 ([Zigmond and Snaith 1983](#)). The HADS is a widely used subject-reported instrument that focuses on subjective disturbances of mood rather than physical signs. The scale consists of 14 items, 7 items each for anxiety and depression. Each item is rated on a 4-point scale based on the frequency of symptoms over the preceding week and ranging from 0 (not at all) to 3 (very often).

Refer to [Section 7.1.4](#) for depression and/or anxiety individual treatment-stopping criteria.

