8.3.8 Adverse Events of Special Interest

AESIs must be monitored on an ongoing basis. These events will be reported with narratives, allowing for the collection of additional information, as warranted. The following may be considered AESIs for this study:

- Significant liver chemistry changes that do not satisfy study drug stopping rules (see [Section 7.1.1](#) and [Section 13.2](#)). Cases of Hy's Law should be reported as SAEs.
- Suicidality as indicated by Type 3, 4, or 5 ideation on the C-SSRS (see [Section 7.1.3](#) regarding study drug stopping criteria for suicidality and [Section 8.2.6.1](#) regarding the C-SSRS). This safety finding will be reported as an AESI if it is not considered an SAE definition (e.g., resulting in hospitalization).
- Depression or anxiety that is moderate or severe (CTCAE Grade 2 or higher), as assessed by the Investigator (see [Section 7.1.4](#) regarding study drug stopping criteria for depression or anxiety). This will be reported as an AESI if it is not considered an SAE (e.g., resulting in hospitalization).
- Adverse events of adrenal insufficiency will be reported on a separate Adrenal Insufficiency Form. Additionally, symptoms of adrenal insufficiency will be reported as SAE if they necessitate parental GC administration by a health care professional and two of the following criteria are met: hypotensive (systolic blood pressure <100 mmHg); nausea or vomiting; severe fatigue; documented hyponatremia, hyperkalemia, or hypoglycemia. If hospitalization was required or the event of adrenal insufficiency is deemed to be an important medical event, life-threatening, results in a persistent or significant disability/incapacity or death, it should also be reported as an SAE.
 - For SAEs of adrenal insufficiency, records from the office of health care provider, emergency facility or hospital the following information should be obtained as source documents to provide the following information:
 - Was stress dosing employed prior to the adrenal insufficiency event? If yes, what were the GC dose and duration of dosing and the cause for stress dosing prior to seeking medical attention?
 - What type, dose and route of parental GC was administered and the duration of administration?

- What concomitant medications were administered?
- What clinical laboratory results are available?
- What AEs occurred?
- What was the duration of stay if admitted to the hospital?

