8.3.15 Quality of Life Assessments and Scoring

8.3.15.1 HADS Anxiety and Depression Scores

The scale consists of 14 items, 7 items each for anxiety and depression. The anxiety score is the sum of the odd-numbered items (questions 1, 3, 5, 7, 9, 11, 13), and the depression score is the sum of the even-numbered items (questions 2, 4, 6, 8, 10, 12, 14). Each item is rated on a 4-point scale based on the frequency of symptoms over the preceding week and ranging from 0 (not at all) to 3 (very often). The sub-scores are the sum of individual item scores within each subcategory (anxiety or depression) and ranges from 0 to 21, with higher scores corresponding to higher levels of anxiety or depression. The total score of the individual item scores and ranges from 0 to 42, with higher scores corresponding to higher levels of anxiety or depression.

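### The SAP derives separate HADS anxiety and depression sub-scores but summarises only their total, in which opposite changes cancel; adding the sub-scores is a nearly free improvement

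*SAP*

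**What the plan says.** SAP 8.3.15.1 defines three HADS quantities. Two are the anxiety and depression sub-scores: "The sub-scores are the sum of individual item scores within each subcategory (anxiety or depression) and ranges from 0 to 21". The third is their sum: "The total score of the individual item scores and ranges from 0 to 42".

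SAP 13.6.1 then carries only the third into the output: "The total score of HADS, change from baseline in total score will be summarized by time point, treatment group, and study period". No other section of the SAP text summarises the sub-scores.

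The protocol never sets a limit on the total.

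- **Entry.** Section 5.1.2 excludes a subject with "HADS score >12 for either depression or anxiety at screening or baseline". Section 7.1.4 restates this explicitly by subscale: "Individuals who score >12 on either the depression or anxiety subscale of the HADS" at either time point are ineligible.
- **On study.** Section 7.1.4 bases study drug discontinuation on a clinical grade: "Any subject who develops severe depression or anxiety (Common Terminology Criteria for Adverse Events [CTCAE] Grade 3 or higher), as assessed by the Investigator". Section 8.3.8 defines the adverse event of special interest in the same way, at a lower grade: "Depression or anxiety that is moderate or severe (CTCAE Grade 2 or higher), as assessed by the Investigator".
- **Output.** Section 9.4.7.7 commits to listing the HADS data. It promises no summary table.

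**The concern.** Depression and anxiety are named as separate conditions wherever the protocol acts on them, and the HADS is the trial's self-reported measure of each. Adding the two sub-scores before summarising discards the distinction. If one worsens while the other improves, the mean change in the total can be near zero in both arms. If one worsens alone, the shift is carried by a noisier quantity and the reader cannot tell which condition moved.

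What is at stake is how well the safety report describes mood by arm. No efficacy conclusion, sample size, error rate or stopping decision depends on it.

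**Working it through.** **Inputs.** From the protocol, section 8.2.6: "The scale consists of 14 items, 7 items each for anxiety and depression", each item scored 0 to 3. From SAP 8.3.15.1: the sub-score and total ranges. From protocol 5.1.2 and 7.1.4: the entry limit of above 12 on either subscale. The documents give no HADS standard deviation and no correlation between sub-scores, so those are assumed below.

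**1. Reproduce the stated ranges.** Sub-score: 7 × 3 = 21. Total: 14 × 3 = 42. Both agree with SAP 8.3.15.1.

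**2. Cancellation.** Take a subject at anxiety 8, depression 8 (total 16) who moves to anxiety 13, depression 3 (total 16). The change in total is 16 − 16 = 0. Anxiety has risen by 5 and now exceeds 12. At group level, a mean change of +2 on one sub-score and −2 on the other gives 0 on the total.

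**3. What a total says about a sub-score above 12.** Each sub-score runs from 0 to 21.

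| Total | Is a sub-score above 12? | Possible pairs with one above 12 |
|---|---|---|
| 12 or less | No | none |
| 13 | Cannot tell | 2 of 14 (13+0 and 0+13) |
| 24 | Cannot tell | 18 of 19 (all except 12+12) |
| 25 or more | Yes | all |

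Totals of 13 to 24 are therefore inconclusive. An eligible subject can have a baseline total of up to 12 + 12 = 24, so this band is the upper part of the eligible baseline range. Of the 22 × 22 = 484 possible score pairs, 484 − 13 × 13 = 315 have a sub-score above 12, and 144 of those (46%) have a total of 24 or less. These are counts of possible pairs, not patient frequencies.

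**4. A change in one sub-score only.** Let both sub-score changes have SD s and correlation r. The SD of the change in total is s × √(2 + 2r). A mean shift d on one sub-score is still a shift d on the total, so its standardised size goes from d/s to d/(s√(2 + 2r)), a factor of 1/√(2 + 2r):

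| r (assumed) | Factor |
|---|---|
| 0 | 0.71 |
| 0.3 | 0.62 |
| 0.5 | 0.58 |
| 0.7 | 0.54 |

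The raw mean is not diluted: +2 on depression alone appears as +2 in the mean total. What falls is its size relative to the spread.

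**The case against.** The strongest reply is that the plan breaks no rule and that mood is reported elsewhere.

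- **The limit of 12 applies at entry only.** A reader might infer that it is an on-study safety criterion which the SAP fails to report. The documents do not support that: on treatment, both discontinuation and the special-interest definition rest on the investigator's CTCAE grade, not on a HADS score. This stands, and it limits how a post-baseline count may be labelled.
- **Other outputs cover part of the gap.** SAP 13.1.2 and 13.1.3 tabulate adverse events, including severe, serious and special-interest events and those leading to discontinuation, by preferred term, so depression and anxiety coded to different terms would appear separately. The protocol promises a HADS listing; SAP 13.6.1 does not repeat that, but its silence does not cancel it. The SAP's summary table already goes beyond the protocol. All of this stands as mitigation. It does not close the gap, because adverse event tables depend on an event being recognised and recorded, and a listing offers no comparison between arms.
- **The loss should not be overstated.** SAP 13.6.1 is descriptive and plans no test, the factor in step 4 rests on assumed values, and nothing in the documents suggests that equal and opposite changes are expected. This stands. A reader might also infer that totals of 13 to 24 carry no information about the limit; the counts at 13 and 24 show that they carry some.
- **The mock shells are not available.** SAP section 8 places presentation conventions in an appendix that is not part of the text reviewed. The statement that only the total is summarised is therefore a statement about the SAP text.

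A reader might further connect the protocol's description of tildacerfont as CNS-active with the HADS. That description is in section 7.1.3, on suicidality, where it supports C-SSRS monitoring. It is not needed here.

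**Conclusion.** The point holds as a low-priority improvement to safety reporting. The SAP text derives the two sub-scores and then summarises only their sum, while the protocol separates anxiety from depression at entry and on study.

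Complete masking needs offsetting changes. A change in one sub-score alone stays visible in the mean but has about 0.54 to 0.71 of its standardised size, given equal SDs and an assumed correlation of 0.7 to 0. The cancellation example and the inconclusive band of 13 to 24 follow from the scoring ranges and need no assumption.

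It would go too far to say that a depression or anxiety signal would go unreported. The adverse event tables and the protocol's listing remain.

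**What to change.** In SAP 13.6.1:

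- Summarise the anxiety and depression sub-scores, as value and change from baseline, by time point, treatment group and study period, alongside the total.
- Add a descriptive number and percentage of subjects with a post-baseline sub-score above 12, separately for anxiety and depression. State that 12 is the protocol's entry limit used as a reporting threshold, and that it is not an on-study stopping or special-interest rule. SAP 13.2 to 13.4 already give threshold counts of this kind for laboratory, vital sign and ECG data.
- Repeat the protocol's commitment to a HADS listing, so that the two documents agree on their face.

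The cost is a few lines of SAP text and an extension of one table, made before database lock. The sub-scores are already derived, and no new data collection or protocol amendment is needed.
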